
4. Genetic Testing N/A

A. Describe

- i. the types of future research to be conducted using the materials, specifying if immortalization of cell lines, whole exome or genome sequencing, genome wide association studies, or animal studies are planned
- ii. the plan for the collection of material or the conditions under which material will be received

Assessment Schedule

SCID, Demographics, Physical exam	Week 0
Urine toxicology, pregnancy test for female subjects	Week 0 and every 4 weeks subsequently + as needed
Fluorescence check in urine for compliance	determined by study physician
Fasting Glucose, Insulin, HbA1c, Lipid Profile, Liver function tests	Week 0, 16, 32, 52
Serum leptin, ghrelin, peptide YY, adiponectin, high sensitivity	Week 0, 16, 52
CRP, interleukin 6	
Framingham Score	Calculated same time with blood draws.
Vitals (Blood Pressure, pulse)	Weekly for first 4 weeks, then every two weeks
Weight, BMI	Weekly for first 4 weeks, then every two weeks
RMR, Waist Circumference (WC), 24hr Food Recall, TFEQ, YPAS, BPRS, BDI, QCSRF, QLS, SF-36, C-SSRS.	Week 0 and every 4 weeks
UKU side effects	Weekly for first 4 weeks, then every two weeks
Cognitive Battery	Week 0, Week 16, Week 52

- iii. the types of information about the donor/individual contributors that will be entered into a database
- iv. the methods to uphold confidentiality

- B. What are the conditions or procedures for sharing of materials and/or distributing for future research projects?
- C. Is widespread sharing of materials planned?
- D. When and under what conditions will materials be stripped of all identifiers?
- E. Can donor-subjects withdraw their materials at any time, and/or withdraw the identifiers that connect them to their materials?
 - i. How will requests to withdraw materials be handled (e.g., material no longer identified: that is, anonymized) or material destroyed)?
- F. Describe the provisions for protection of participant privacy
- G. Describe the methods for the security of storage and sharing of materials

5. Subject Population: Provide a detailed description of the types of human subjects who will be recruited into this study.

200 patients with severe mental illness

6. Subject classification: Check off all classifications of subjects that will be specifically recruited for enrollment in the research project. Will subjects who may require additional

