Data will be electronically scanned into databases and will be double checked by hand. Hard copy documents will be examined to verify questionable observations. Missing data will be examined for each variable. Histograms, normal probability plots, and numerical summaries (skewness, kurtosis) will be used to examine distributional assumptions required for the mixed model analysis described below. Transformations such as the logarithm, square root, and reciprocal will be considered in the event the normality assumption is inadequate. Residual analysis will also be performed to evaluate distributional variance and linearity assumptions. Data analysis will be conducted in collaboration with [name], statistician in the department of Psychiatry and [name] faculty member of the Department of Biostatistics at Yale University School of Public Health. For all analyses, an alpha threshold of 5% (two-sided) will be used to test for statistical significance and will be performed using SAS v9.3 (SAS Institute, Cary, NC).

Analyses will be performed according to the intent-to-treat (ITT) principle where data from any randomized subjects will be analyzed. We will calculate descriptive statistics for participants at baseline, and compare naltrexone to placebo participants using analysis of variance (ANOVA) for normally distributed covariates and chi-square tests for categorical covariates. The impact of baseline variables that demonstrate clinically relevant group differences will be assessed in supportive analyses using covariate adjustment.

Approach to Missing Data: The primary analysis method will use a likelihood-based mixed model, which accommodates incomplete observations and operates under the assumption that the missing data is missing at random (MAR). Missing data patterns, time to withdrawal and reasons for dropout will be compared between the two naltrexone and placebo groups. T-tests, cross-tabulations, and logistic regression will be used to evaluate whether withdrawal is dependent on any observed variables. Finally, should missing data patterns and reasons for missing data suggest a bias or confounding, we will conduct sensitivity analyses using pattern mixture models to examine the influence that dropout bias (informative missingness) may have on treatment differences. Multiple imputation (MI) will also be used in the case of data not MAR. Sensitivity analyses will be performed secondarily among study completers.

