Other Outcomes: Schizophrenia symptoms (BPRS), depression (BDI), dietary consumption (TFEQ), exercise (YPAS), quality of life (Q-LES-Q and SF-36), cognition (MATRICS) and metabolism/inflammation markers will be obtained as presented in table 3. Summary statistics (frequencies, percents, means and standard deviations, and medians and interquartile ranges) will be calculated for naltrexone vs. placebo at each time point. Appropriate parametric (for normally distributed data) and non-parametric (deviation from normality in data distribution) approaches will be used to ascertain clinically meaningful group differences at each time point. Depending upon the distribution of these outcomes, the effect of naltrexone vs. placebo on change over time in each outcome will also be examined with GLMM, making appropriate model selections for either binary or continuous outcomes.

Using UKU Side Effect Checklist and C-SSRS we will list and summarize side effects and suicidal tendencies reported in each treatment group. Medication changes that could not be avoided during the study will be examined in three groups: no change, change from a higher weight liability to a lower weight liability medication, and vice versa. Weight liability rankings of antipsychotics will be based on Allison and Newcomer. Distributions of all variables will be evaluated for normality. Alternative statistical approaches such as transformations or non-parametric tests will be used, as required.

SECTION VI: RESEARCH INVOLVING DRUGS, BIOLOGICS, RADIOTRACERS, PLACEBOS AND DEVICES

A. DRUGS, BIOLOGICS and RADIOTRACERS

- 1. Identification of Drug, Biologic or Radiotracer:** What is (are) the name(s) of the drug(s) biologic(s) or radiotracer(s) being used? Identify whether FDA approval has been granted and for what indication(s).

Naltrexone is an FDA approved medication with the indication of alcohol dependence.

All protocols which utilize a drug, biologic or radiotracer **not** approved by, but regulated by, the FDA, or a radiotracer regulated by the RDRC, must provide the following information:

- a. What is the Investigational New Drug (IND) **number** assigned by the FDA? N/A
- b. Who holds the IND?
- c. All protocols which utilize a radiotracer not approved by, but regulated by the FDA must provide the IND number: _____
Alternatively, use of the investigational radiotracer may be under RDRC/RSC oversight: (check if appropriate) _____

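### Other outcomes are compared between groups at each scheduled assessment at an unadjusted 5% level, with no ranking against the longitudinal model planned for the same outcomes

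*Combined protocol and SAP*

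**What the plan says.** The Other Outcomes paragraph of Section V, item 12 lists the outcomes as "Schizophrenia symptoms (BPRS), depression (BDI), dietary consumption (TFEQ), exercise (YPAS), quality of life (Q-LES-Q and SF-36), cognition (MATRICS) and metabolism/inflammation markers". It plans three things for them:

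- summary statistics by group at each time point;
- parametric or, where the data depart from normality, non-parametric "approaches will be used to ascertain clinically meaningful group differences at each time point";
- a longitudinal analysis, in which the effect of naltrexone versus placebo on "change over time in each outcome will also be examined with GLMM".

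The opening paragraph of item 12 sets the level: "For all analyses, an alpha threshold of 5% (two-sided) will be used to test for statistical significance". The Hypothesis Testing paragraph applies a Bonferroni correction to secondary outcomes, giving BMI, waist circumference, lipids, glucose and HbA1c as examples. The Other Outcomes paragraph states no adjustment, no key time point, no order between the two analyses and no threshold for a clinically meaningful difference.

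The Assessment Schedule places "TFEQ, YPAS, BPRS, BDI, QCSRF, QLS, SF-36, C-SSRS" at "Week 0 and every 4 weeks". The cognitive battery is at "Week 0, Week 16, Week 52", and the leptin-to-interleukin marker panel is also at weeks 0, 16 and 52.

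**The concern.** The per-assessment comparisons are more than description. Summary statistics at each time point are already covered by the preceding sentence, and choosing between parametric and non-parametric methods by normality is the language of testing. With a blanket 5% level and no adjustment, the plan produces many tests per outcome alongside a longitudinal analysis of the same data. If the two disagree, nothing says which one counts.

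The stakes are highest for the BPRS and BDI. The Research Plan (Section V, item 3) uses the BPRS to show that treatment does not worsen the illness, and the Risks section (item 9) names depression as a possible naltrexone effect. An isolated difference at one mid-study assessment could be reported as harm or as benefit, with no rule for weighing it against the longitudinal result. Letting the data choose the test at each assessment adds a further analytic choice.

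**Working it through.** The plan gives no number of tests, error rate or power for these outcomes, so there is no figure of its own to reproduce.

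**Inputs**
- Level: 0.05 two-sided (item 12, opening paragraph).
- Scales named under Other Outcomes and scheduled four-weekly: BPRS, BDI, TFEQ, YPAS, Q-LES-Q and SF-36, so 6. This reads QLS in the schedule as Q-LES-Q and counts one total per scale.
- Post-baseline assessments: weeks 4, 8, ..., 52, so 52/4 = 13.
- The text refers to a table 3. No table with that label appears in the text available, so the Assessment Schedule was used.
- Correlations: not given, so assumed and shown as a range.

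**Expected number of chance findings under the null.** This does not depend on correlation.
- Tests per contrast: 6 x 13 = 78.
- Expected: 78 x 0.05 = 3.9.
- If each dose is tested against placebo: 156 tests and 7.8 expected.

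**Probability of at least one, and of three or more, per contrast.** If all 78 tests were independent, P(at least one) = 1 - 0.95^78 = 98%. Independence is unrealistic, so correlated null test statistics were simulated (40,000 replicates, critical value 1.96):

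| Within-scale correlation | Between-scale correlation | P(at least 1) | P(3 or more) |
|---|---|---|---|
| equal, 0.5 | 0 | 91% | 60% |
| autoregressive, 0.8 | 0 | 89% | 60% |
| equal, 0.8 | 0.5 | 61% | 37% |

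Under the autoregressive 0.8 case a single scale has a 31% chance of at least one false positive. For BPRS and BDI together, taken as independent, this is 1 - 0.69^2 = 52%. Chance findings cluster: in the same case three or more different scales are flagged in only 27% of replicates.

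**Wider counts**
- Adding cognition (one composite, assumed) and six markers at weeks 16 and 52: 78 + 7 x 2 = 92 tests, 4.6 expected.
- Replacing the TFEQ and SF-36 totals by their 3 and 8 subscales: (4 + 3 + 8) x 13 + 14 = 209 tests, 10.45 expected.
- Both doses with subscales: 418 tests, 20.9 expected.

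**After moving inference to one longitudinal contrast per outcome**
- 13 outcomes (6 scales, cognition, 6 markers): 13 x 0.05 = 0.65 expected.
- P(at least one) = 1 - 0.95^13 = 49% if independent.
- With Bonferroni at 0.05/13: 1 - (1 - 0.05/13)^13 = 4.9%.

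The longitudinal model therefore reduces the problem considerably but does not control the family error rate by itself.

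**The case against.** These outcomes lie outside Hypotheses 1 and 2, sit in a separate tier and already have a longitudinal model, so the consequences are limited. That stands and keeps the point minor.

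Several stronger readings are tempting, but the documents do not support them:

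- **Several chance findings are near certain.** The 89% to 91% figures are for at least one. Three or more have about 37% to 60% probability for six scale totals and one contrast. Near certainty would need both doses and the subscales to be tested, which the paragraph does not specify.
- **Testing happens at every visit.** Visits are weekly and then every two weeks; these outcomes are measured four-weekly, or at weeks 16 and 52.
- **Each dose is tested separately.** The paragraph speaks of naltrexone versus placebo. Dose-specific contrasts are specified for weight at week 52.
- **The comparisons ignore baseline and use only subjects present.** The text does not say whether raw scores, change scores or adjusted values are compared, nor how missing values are handled. Available-case testing is plausible but not stated.
- **A p-value is equated with clinical meaning.** The text does not say so. The gap is that no threshold is given.

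A fair counter-argument concerns safety: a single week-52 contrast could hide transient mid-study worsening in BPRS or BDI. This stands, and it is why per-assessment estimates should be kept rather than removed.

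**Conclusion.** The point holds as an inexpensive improvement. The plan provides two unranked analyses of the same outcomes, one of them repeated at each scheduled assessment at 5% with no stated adjustment. For the six four-weekly scales this means 78 comparisons and 3.9 expected chance findings per contrast under the null. At least one is likely (about 61% to 91%); three or more is roughly an even chance or somewhat either side (37% to 60%).

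The expected count rests on applying the 5% level to each comparison, on one total per scale and on the QLS reading. The probabilities also rest on assumed correlations of 0.5 to 0.8 within and 0 to 0.5 between scales. Separate dose contrasts, if used, would double the number of tests and the expected count. The primary weight analysis is not affected.

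**What to change.** In the Other Outcomes paragraph:

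1. Make the planned longitudinal model, including the baseline value, the only inferential analysis for each outcome. Name its contrasts in advance, for example at week 52 to match the Hypothesis Testing paragraph, and say whether they are pooled or by dose.
2. Report group differences at each assessment as model-based estimates with 95% confidence intervals, marked as descriptive. Drop the per-assessment tests and the normality-based switching.
3. Either label the family exploratory or extend the existing Bonferroni rule to it. Without one of these, 13 unadjusted contrasts still carry the 49% computed above.

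The cost is SAP wording and somewhat less analysis. No p-values would be available at intermediate assessments, but keeping the estimates and intervals for BPRS and BDI leaves any transient worsening visible.

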Subjects will be randomized to active Naltrexone 25mg, Naltrexone 50mg, and placebo groups in a 1:1:1 ratio using a computer randomization procedure at the CMHC research pharmacy, blind to both research team and subjects. Separate randomization schedules will be applied based on gender, and antipsychotic agent to yield an equal number of male and female subjects in each arm. This is to control for possible differential gender and racial/ethnicity specific effects of Naltrexone on weight as well as differences brought on by higher and lower weight liability medications.

Subjects will take the study medication daily for 52 weeks. Subjects will be seen weekly for the first 4 weeks of the study, thereafter they will be seen on a bi-weekly (every other week) basis to be assessed (i.e. weight, side effect check, paper questionnaires) throughout the remaining 48 weeks of treatment. Compliance will be monitored by pill counts as well as 25mg riboflavin added to the capsules which provides florescence to urine under Wood's lamp (UV or black light). Subjects will be given a study identification card listing the fact that they may be taking naltrexone and this card will include the study emergency cell phone number which will be available 24 hours a day, 7 days per week in case of an emergency.

The study is planned to be run at the Connecticut Mental Health Center (CMHC) and its affiliated satellite clinics throughout the greater New Haven area.

All participants will be carefully assessed with physical examination and laboratory findings, any medical problems that need immediate attention will be referred to each participant's own primary care physician. All potential subjects will meet with study staff for intake and evaluation sessions to determine eligibility prior to enrollment.

A description of assessments is given below:

1) Intake interview including demographics, clinical history, Structured Clinical Interview for DSM-IV (**SCID**) to ascertain diagnosis. 2) Urine toxicology (**Utox**) screen to rule out substance use. The initial sample will also be sent to the lab to confirm opiate results for safety purposes and a follow-up sample will be taken immediately before randomization to study medication to ensure it is negative for opiates; continued random testing will occur at the discretion of the study physician throughout the trial along

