Reduced efficacy of opioid medications with naltrexone: Patients taking naltrexone may not benefit from opioid containing medicines, such as cough and cold preparations, antidiarrheal preparations, and opioid analgesics. In an emergency situation when opioid analgesia must be administered to a patient taking naltrexone, the amount of opioid required may be greater than usual, and the resulting respiratory depression may be deeper and more prolonged. Study participants will carry an information card to be used in case of an emergency.

Small increased risk of depression, suicidal ideation, and suicide: Based on data from placebo controlled trials in patients with alcohol and/or opiate dependence there was observed an infrequent however small increased incidence of depression, suicidal ideation, attempts, and completed suicides in the naltrexone treated group compared to the placebo group.

Other Side Effects: In an open label safety study with approximately 570 individuals with alcoholism receiving naltrexone, the following new-onset adverse reactions occurred in 2% or more of the patients: nausea (10%), headache (7%), dizziness (4%), nervousness (4%), fatigue (4%), insomnia (3%), vomiting (3%), anxiety (2%) and somnolence (2%).

Exposure to Naltrexone during Pregnancy: Naltrexone is a pregnancy Category C medication meaning the drug should be given to patients only if the potential benefit justifies the potential risk to the fetus. There is no data on the use of naltrexone or other opioid antagonists in pregnant women. The effects, if any, on the developing fetus are unknown. We will require that female patients of child bearing age use contraception to prevent pregnancy during participation in the study and will not enroll participants who are pregnant or who are trying to get pregnant.

Urine collection

Urine specimens are collected for research assessments and should pose no appreciable risks, and will be done using established procedures already in place at CMHC.

Blood collection

Subjects participating in these studies will have multiple blood draws using established procedures in the CMHC. The blood draw has the risk of producing a bruise at the venipuncture site, and rarely development of a small infection.

Cognitive Assessments, Rating Scales and Questionnaires

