SECTION VII: RECRUITMENT/CONSENT AND ASSENT PROCEDURES

1. Targeted Enrollment: Give the number of subjects:

a. targeted for enrollment at Yale for this protocol 200

b. If this is a multi-site study, give the total number of subjects targeted across all sites N/A

2. Indicate recruitment methods below. Attach copies of any recruitment materials that will be used.

- Flyers
- Posters
- Letter
- Medical Record Review
- Departmental/Center Newsletters
- YCCI Recruitment database
- Other (describe): Clinician Referrals

- Internet/Web Postings
- Mass E-mail Solicitation
- Departmental/Center Website
- Departmental/Center Research Boards
- Web-Based Clinical Trial Registries
- Clinicaltrials.gov Registry (do not send materials to HIC)

- Radio
- Telephone
- Television
- Newspaper

3. Recruitment Procedures:

a. Describe how potential subjects will be identified.

Potential subjects will either self-identify by seeing a flyer and contacting us with their interest, or their clinician may identify them as potentially eligible and give them our contact information. Familiar patients who have done multiple studies with us or who are patients of [name] may be identified by research staff as potentially eligible.

b. Describe how potential subjects are contacted.

Potential subjects will contact research staff in order to complete a telephone screening procedure that will determine eligibility. At that point, we will get permission from the patient to contact them further about the study, via telephone or through their clinician. If a potential subject has been in one of our studies in the past and has given permission to be contacted about future studies, research staff will call them to see if they are interested.

c. Who is recruiting potential subjects?

[name], [name], [name], [name], [name], [name]

4.

Screening Procedures

- a. Will email or telephone correspondence be used to screen potential subjects for eligibility prior to the potential subject coming to the research office? Yes No
- b. If yes, identify below all health information to be collected as part of screening and check off any of the following HIPAA identifiers to be collected and retained by the research team during this screening process.

HEALTH INFORMATION TO BE COLLECTED:

HIPAA identifiers:

- Names

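### The safety summary makes no allowance for length of follow-up, so later-onset events such as suicidality can be understated in an arm with more dropout

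*Combined protocol and SAP*

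**What the plan says.** The analysis of the side-effect checklist (UKU) and the suicidality scale (C-SSRS) is one sentence in Section V, item 12, Other Outcomes: "Using UKU Side Effect Checklist and C-SSRS we will list and summarize side effects and suicidal tendencies reported in each treatment group". It names no denominator, person-time, time-to-first-event method or confidence interval. The per-time-point summaries and the mixed model in the paragraph before it cover symptoms, depression, eating, activity, quality of life, cognition and blood markers. UKU and C-SSRS are not in that list.

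Follow-up is long and ratings repeat. Under Section V, item 3, "Subjects will take the study medication daily for 52 weeks". The Assessment Schedule rates UKU weekly to week 4 and then every two weeks, and C-SSRS at week 0 and every four weeks.

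The plan expects withdrawal. Item 12, Approach to Missing Data, states: "Missing data patterns, time to withdrawal and reasons for dropout will be compared between the two naltrexone and placebo groups". The methods named there are the likelihood-based model, pattern-mixture models and multiple imputation. None is tied to the safety summary.

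Section V, item 9 (Risks) describes suicidality as a known naltrexone risk, reporting from earlier trials a "small increased incidence of depression, suicidal ideation, attempts, and completed suicides in the naltrexone treated group compared to the placebo group".

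**The concern.** A subject can report an event only while being seen. Someone who leaves at week 8 has far fewer ratings than someone who completes the year, yet counts as one full subject in a simple proportion of everyone randomised. If one arm loses subjects sooner, its proportion falls for that reason alone.

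The outcomes most exposed are those that can start at any time in the year, suicidal ideation and behaviour above all. The protocol singles out this risk and uses the C-SSRS to monitor it. The list and summary is the only analysis by arm planned for that scale. The distortion could understate an excess on naltrexone, or suggest one if placebo subjects left sooner.

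**Working it through.** **No plan figure to reproduce.** The documents give no 52-week dropout rate, no event rate by arm for this population and no precision for safety. Risks and dropout rates below are assumptions. The arm size follows from "targeted for enrollment at Yale for this protocol 200" and "Naltrexone 25mg, Naltrexone 50mg, and placebo groups in a 1:1:1 ratio": 200/3, about 67.

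**Opportunity to report.** On-drug UKU ratings: 4 weekly, then weeks 6, 8, …, 52, which is 24 more, so 28. On-drug C-SSRS ratings: 52/4 = 13. A subject leaving at week 8 has UKU at weeks 1, 2, 3, 4, 6 and 8 (6 of 28) and C-SSRS at weeks 4 and 8 (2 of 13).

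**Events spread over the year.** Let the event hazard be h = −ln(1 − 0.10) = 0.1054 per year in every arm, and the dropout hazard be c = −ln(1 − dropout), independent of the event.

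- Observed proportion = h/(h+c) × (1 − exp(−(h+c)))
- Mean time observed, ignoring events = dropout/c

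| One-year dropout | c | Observed proportion | Subjects of 67 | Mean years observed |
|---|---|---|---|---|
| 20% | 0.223 | 8.98% | 6.0 | 0.896 |
| 40% | 0.511 | 7.87% | 5.3 | 0.783 |
| 50% | 0.693 | 7.26% | 4.9 | 0.721 |

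Ratios to the 20% arm are 7.87/8.98 = 0.88 and 7.26/8.98 = 0.81. They are nearly the same at a 5% or 20% one-year risk (0.87 to 0.88, and 0.81). A Kaplan-Meier estimate at week 52 targets 10% in every row.

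**How large a true excess could be offset.** Raising h in the high-dropout arm until its proportion equals 8.98% gives a hazard ratio of about 1.15 at 40% dropout and 1.25 at 50%. A true hazard ratio of 1.5 at 20% against 50% dropout shows as 10.64/8.98 = 1.18, compared with 1.46 when dropout is 20% in both arms. With 20% dropout on placebo, offsetting it fully would take about 67% dropout on naltrexone; a hazard ratio of 2.0 would take about 84%.

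**Equal dropout.** For a true hazard ratio of 1.5, the ratio of proportions is 1.46 at 0%, 20% or 30% dropout in both arms. Dropout as such does no harm to the comparison; a difference in dropout does.

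**Early-onset events.** Put the whole 10% risk, equal in all arms, into the first T = 4/52 year, so the hazard there is 0.1054/T = 1.370.

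- Observed proportions at 20%, 40% and 50% dropout: 9.92%, 9.81%, 9.74%. Ratios are 0.99 and 0.98, so the simple proportion is nearly right.
- Mean person-years to first event or exit: 0.810, 0.708, 0.653. Rates per person-year: 0.0992/0.810 = 0.122, 0.0981/0.708 = 0.138, 0.0974/0.653 = 0.149. Rate ratios to the 20% arm are 1.13 and 1.22, a false excess in the arm that leaves earlier.
- Share of attended visits has the same fault. Nausea at weeks 1 and 2 is 2/28 = 7% of visits for a completer and 2/6 = 33% for someone who leaves at week 8.

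The choice of summary therefore matters: a person-year rate repairs the first case and damages the second, while the Kaplan-Meier cumulative incidence is sound in both.

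**The case against.** The plan never says it will use crude proportions of all randomised subjects. That is inferred from its silence, and a by-visit summary would also fit the sentence. This stands. The gap is that the method is not stated, and the figures above describe its most natural reading.

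Nothing in the documents supports dropout of 20% against 40% to 50%. The only trial dropout figure (Section V, item 2, pilot study) is 1 of 24 over 8 weeks, on placebo and for personal reasons. Escalating monthly payments (Section X) favour retention in every arm. This also stands: neither the size nor the direction of any imbalance is known. Carried forward at a constant hazard, the pilot figure gives 1 − (23/24)^6.5, about 24% at one year, so a 20% base rate is not inflated. It says nothing about a difference between arms.

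Sampling error is larger than the bias. The shifts are 1.1 and 1.7 percentage points, about one subject of 67. The standard error of the difference, √(0.0898×0.9102/67 + 0.0787×0.9213/67), is about 4.8 points. Power for 10% against 20% is only 37% before any dropout. That limits the practical effect, but does not justify leaving a removable distortion in the safety display.

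There are partial safeguards. Comparing time to withdrawal by arm would reveal unequal follow-up, depression scores get a longitudinal model, and suicidal thoughts prompt individual assessment and referral. None of these corrects the safety table.

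A reader might also infer that naltrexone subjects, especially at the higher dose, will leave sooner because of nausea. The documents do not show this. The nausea (10%) and vomiting (3%) figures in the Risks section come from one open-label study with no dose comparison, no placebo arm and no discontinuation rate. Section VI, under Dosage, reports no dose or pattern of dosing shown to be better than another at reducing such complaints for all patients.

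**Conclusion.** The point holds as a conditional one. The plan sets no method that accounts for follow-up time in its only by-arm summary of UKU and C-SSRS. If dropout differs between arms, later-onset events can be understated in the arm with less follow-up. Under an assumed 10% one-year risk, constant hazards, dropout independent of the event, and 20% against 40% to 50% dropout, the understatement relative to the other arm is 12% to 19%.

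The distortion is negligible with equal dropout and for early effects, which are mostly on record before a subject leaves. It would be going too far to infer that a real naltrexone excess would disappear: under these assumptions that happens only for hazard ratios of about 1.15 to 1.25, and larger excesses are attenuated. The direction is unknown and could run against either drug or placebo. This is an inexpensive improvement to safety reporting and does not touch the primary analysis.

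**What to change.** In Section V, item 12, Other Outcomes, specify the following by arm (25 mg, 50 mg, placebo), for each C-SSRS ideation and behaviour category and for a named list of key UKU effects:

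- the number and percentage of subjects with the event, with the denominator and the total follow-up time;
- a Kaplan-Meier (visit-based life-table) cumulative incidence of first event to week 52, with a confidence interval.

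Do not make events per person-year or share of attended visits the main summary for early-onset effects, because either can create a false excess in the arm that leaves earlier.

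The cost is some wording and one extra table or plot. The ratings are already scheduled, so no new data are needed. The intervals will be wide because events are few, and the estimate assumes that leaving the study is not driven by the event itself. The planned comparison of reasons for dropout by arm should be read beside it for that reason. The wording should be settled before unblinding, so that the denominator is not chosen with results in view.
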